**G. Potential Direct Benefits to Subjects**

There are no direct benefits to subjects from their participation in this research.

## 5.0 Special Considerations

### 5.1 Health Insurance Portability and Accountability Act (HIPAA)

This study will record name, date of birth, and sex. Authorization for PHI utilization is detailed in the written consent form.

### 5.2 Family Educational Rights and Privacy Act (FERPA)

NA.

### 5.3 Code of Federal Regulations Title 45 Part 46 (Vulnerable Populations)

NA

#### A. Special Populations

### 5.4 General Data Protection Regulation (GDPR) -

### 5.5 NJ Access to Medical Research Act (Surrogate Consent)

NA

## 6.0 Data Management Plan

### 6.1 Data Analysis

Rutgers RUBIES will conduct a priori power analysis for determining the appropriate sample size. Functional outcome measures (ROM, strength, muscle endurance) will be analyzed via Student's t test. PROMs (IHOT, mHHS, VAS, PROMIS-10) will be analyzed via Wilcoxon unranked sum test.

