#### A. Research Procedures

The project will be a randomized control trial where all patients who present to our office with groin based hip pain, radiographic evidence of FAI, and a positive anterior impingement test would be recruited. Two groups will then be separated: one being the traditional physical therapy group, and the other with the addition of BFR to traditional PT.

Standard radiographs would be obtained and would include a standard AP pelvis, Dunn view, and false profile view.

Initial office visit would record the patient's degree of hip flexion, result with anterior impingement testing, alpha angle (on dunn view), lateral center edge angle (on AP pelvis) and anterior center edge angle (on false profile view). Additionally, we would evaluate for the presence of ischial spine sign, cross over sign, and if the proximal femoral physis was present on radiographs. MRI will not be routinely ordered on the initial visit, but if this has already been obtained, the presence of a labral tear based on the radiology report will be recorded.

Demographic data would be collected which would include age, sex, primary sport, duration of symptoms, and previous treatment.

Physical therapy protocol would include traditional PT focusing on core and gluteal strengthening. Additionally, avoidance of activities and exercises that result in pain or high hip flexion and internal rotation would be recommended. After 6 weeks, if the patient remained symptomatic, an ultrasound guided intra-articular hip injection would be offered to the patient. If the patient remained persistently symptomatic, then hip arthroscopy would be offered to the patient.

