**1.5 Sample Size Justification**

Previous similar studies have recruited 35 to 60 subjects for similar studies looking at functional outcomes with BFR treatment. We are conducting an a priori power analysis with Rutgers RUBIES to determine the sample size required for 80% power with an alpha of 5%.

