**1.9 Data Collection**

**A. Primary Data Collection**

Data will be collected by Physical Therapists during their treatment visits at a UOA physical therapy clinic.

- **Location:** - UOA, Non-Rutgers approved facility, recorded via RedCap Survey Tool
- **Process of Data Collection:**Data will be collected by physical therapists providing standard patient care. .
- **Timing and Frequency:** Pre/Post intervention, PROMs – Pre, 2, 4, 8 weeks.
- **Procedures for Audio/Visual Recording:** NA
- **Study Instruments:**
  - **VAS** – Visual Analog Pain Scale – ( 0-10)
  - **PROMIS-10** – Pre/Post intervention
  - **Modified Harris Hip Score** – Pre/Post intervention

- IHOT-12 – Pre/Post Intervention
- **Ethnographic Studies, Interviews, Or Observation:**
- **Subject Identifiers** – Upon volunteering for the study, patients will be assigned a study number. All data collected will be associated with the no personal identifiers.

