**Data Abstraction Form(s):**

**1.10 Timetable/Schedule of Events**

Subjects will be advised of the study by referring Physician. Potential participants will be referred to physical therapy and notified of study. After private review, and answering of all questions, the subjects will volunteer to participate, and sign consent form. Pre-Intervention PROMs will be completed prior to involvement in the study. Supervising physical therapists will collect Baseline pre-intervention assessment including measurement of ROM, strength and endurance as measured by Microfet handheld dynamometer @weej 2, 4, 8 week intervals.. VAS will be collected by PT @ week 2, 4, 8 week intervals. PROMs will be repeated at the completion of physical therapy program.

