#### 4.2 Obtaining Identifiable Information About Non-Subjects NA

#### 4.3 Number of Subjects

##### A. Total Number of Subjects

A review completed by RUBIs determined that 26 subjects is needed to make formal determination of validity.

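### Section 6.1 makes no stated use of the baseline values the trial collects and misnames one test; a between-arm ANCOVA would be more precise at almost no cost

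*Protocol*

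**What the plan says.** Section 6.1 is the only analysis text in the protocol. For the functional outcomes it says "Functional outcome measures (ROM, strength, muscle endurance) will be analyzed via Student's t test". For the patient-reported outcomes it says "PROMs (IHOT, mHHS, VAS, PROMIS-10) will be analyzed via Wilcoxon unranked sum test". It does not state whether the t test is paired or two-sample, whether the week-8 value or the change is tested, or which visit counts. It names no covariate.

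Baseline values are collected. Section 1.10 says "Supervising physical therapists will collect Baseline pre-intervention assessment including measurement of ROM, strength and endurance". Section 1.9 A gives the general timing as "Pre/Post intervention, PROMs – Pre, 2, 4, 8 weeks" and lists, for example, "IHOT-12 – Pre/Post Intervention". Section 1.6 B has endurance measured before as well as after training and includes an initial VAS.

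The design is a randomised comparison of two groups. Section 1.3 A says "Two groups will then be separated: one being the traditional physical therapy group, and the other with the addition of BFR to traditional PT". On size, Section 4.3 A says "A review completed by RUBIs determined that 26 subjects is needed to make formal determination of validity".

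**The concern.** There are two separate problems.

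The first is the name. Two Wilcoxon tests are in common use: the rank-sum test for independent groups and the signed-rank test for paired values. An unranked sum test is neither, so the patient-reported outcomes cannot be analysed as literally written. Someone has to decide what was meant, and that is better done before outcome data are seen.

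The second is precision. With about 13 subjects per arm, precision is the main limit on what the trial can show. A t test on week-8 values carries the full between-person variance and any chance difference between the arms at baseline. Adjusting for baseline removes the part of that variance that baseline predicts. The measurements are already being taken, so not using them gives away power for nothing.

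**Working it through.** **Inputs from the protocol.** Total 26 (Section 4.3 A); two randomised groups (Section 1.3 A). Section 1.5 plans a power analysis "to determine the sample size required for 80% power with an alpha of 5" per cent.

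**Assumptions, because the protocol is silent.** 1:1 allocation, so 13 per arm; a two-sided level; no dropout; a correlation r between baseline and week 8 of 0.3 to 0.8; equal SD at both times. All differences are in units of that SD.

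**The plan's own figure.** The 26 cannot be reproduced, because no outcome, effect size or SD is given. It can be solved backwards.
- Normal approximation: detectable difference = (1.960 + 0.842) × √(2/13) = 2.802 × 0.392 = 1.10 SD. In the other direction, n per arm = 2 × 2.802² / 1.1² = 12.98, rounded up to 13, which gives 26.
- Exact noncentral t with 24 degrees of freedom: 1.145 SD. At a true 0.8 SD the noncentrality is 0.8 × √(13/2) = 2.04 and the power is 50%.

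**ANCOVA.** The residual SD is √(1 − r²). Estimating the slope costs one degree of freedom (leaving 23) and inflates the SD by about √(1 + 1/22) = 1.022. On 23 degrees of freedom the multiplier for 80% power is about 1.147, so detectable difference = 1.147 × 1.022 × √(1 − r²). For r = 0.5 this is 1.147 × 1.022 × 0.866 = 1.02.

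**t test on change.** The SD of change is √(2(1 − r)), so detectable difference = 1.145 × √(2(1 − r)). For r = 0.7 this is 1.145 × 0.775 = 0.89.

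| r (assumed) | t test, week-8 value | t test, change | ANCOVA | Power at 0.8 SD: week-8 value | Power at 0.8 SD: ANCOVA |
|---|---|---|---|---|---|
| 0.3 | 1.145 | 1.36 | 1.12 | 50% | 52% |
| 0.5 | 1.145 | 1.15 | 1.02 | 50% | 60% |
| 0.7 | 1.145 | 0.89 | 0.84 | 50% | 76% |
| 0.8 | 1.145 | 0.72 | 0.70 | 50% | 89% |

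Change is worse than the week-8 value at r = 0.3, equal to it at 0.5, and better above that. ANCOVA is the most precise of the three in every row.

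**Chance imbalance.** The baseline difference between arms has SD √(2/13) = 0.39, so it exceeds 0.5 SD in either direction with probability of about 20%.

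These figures are for the t test and ANCOVA on approximately normal outcomes. No separate calculation was made for the rank test.

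**The case against.** **The wrong name is a slip.** Largely accepted. The word sum survives in it, and among the Wilcoxon tests that word belongs to the rank-sum test for independent groups. Changing one word settles the matter, but the word still has to be changed.

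**A two-sample t test is valid under randomisation, and covariates are commonly left to an SAP, which may exist.** Both parts stand. The absence of ANCOVA is not an error, and the case for it is better use of data already collected. The gain also depends on r: at 0.3 it is nearly nothing.

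**The tests may not be unadjusted.** This also stands. Section 6.1 does not exclude a two-sample t test on change, which uses baseline. At r = 0.7 it detects 0.89 SD against 0.84 SD for ANCOVA, so much of the gain might already be intended. It remains behind ANCOVA throughout and loses to the plain week-8 comparison below r = 0.5.

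**A stronger reading that a reader might infer.** Section 6.1 names no contrast, and the data collection text speaks of pre and post. One might conclude that the trial will test change within each arm and compare significance. That would not estimate the effect of BFR. With 13 per arm and both arms improving equally by 0.3, 0.5 or 0.8 SD of change, paired t tests have power of 0.169, 0.382 and 0.754. The chance p(1 − p) of significance with BFR only is then 14%, 24% and 19%. The documents do not support this reading. Sections 1.1 A, 1.1 B, 1.3 and 1.3 A set out a randomised comparison of BFR added to physical therapy against physical therapy alone. The pre/post wording in Section 1.9 A says when data are collected, not what is compared. Within-arm testing is nowhere prescribed.

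**Conclusion.** The point holds as a recommended improvement together with a correction of the test name. Section 6.1 names a test that does not exist, and neither of its tests is stated to use the baseline values collected. Under the stated assumptions, baseline-adjusted ANCOVA lowers the detectable difference from 1.145 SD to between 1.12 SD (r = 0.3) and 0.70 SD (r = 0.8). For r of 0.5 to 0.7, power at 0.8 SD goes from 50% to between 60% and 76%. Those sizes rest on 13 per arm, a two-sided 5% level and an r that the protocol does not give.

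The finding does not show that the planned analysis is invalid, that baseline is certainly ignored, or that a within-arm comparison is intended. It does not justify treating the change as one without which the trial cannot proceed.

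**What to change.** Amend Section 6.1 before outcome data are examined:

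- State that each outcome is compared between the randomised arms at week 8 by ANCOVA, with the baseline value of the same outcome as covariate, and reported with a 95% confidence interval.
- Correct the name to the Wilcoxon rank-sum test (two-sample, between arms) and keep it for the patient-reported outcomes, either on change from baseline or as a rank-based ANCOVA. State in advance which form is used and how it stands beside the ANCOVA estimate. By analogy with the t test, change may lose precision if the correlation is below about 0.5.
- State that within-arm pre/post tests are descriptive only.

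A mixed model using the week 2 and week 4 visits is optional and not part of this point.

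The cost is a few sentences and one degree of freedom (23 instead of 24). It needs no further subjects, visits or measurements.

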### 6.2 Data Security

All collected data will be recorded directly to REDCap by study members at the time of the research visit. Access to REDCap will be password-protected and limited to only study team members, and data recording will be performed on password-protected computers at UOA sites. Paper copies of data will not be kept. Data will be kept on REDCap for 6 years after which it will be deleted.

### 6.3 Data and Safety Monitoring

NA

**A. Data/Safety Monitoring Plan**

Input of data will be periodically monitored by the study coordinator to ensure complete data collection within RedCap.

**B. Data/Safety Monitoring Board Details**

In the event of a significant issue, the PI, Study coordinator, and supervisor of Physical Therapy will discuss and appropriately resolve the issue. Any significant issues will be reported directly to the IRB.

**6.4 Reporting Results**

**A. Individual Subjects' Results**

Study results will not be shared with subjects anyone else.

**B. Aggregate Results**

Study results will be shared upon request of subjects at the completion of the study.

**C. Professional Reporting**

Once the data has been gathered, analyzed, and conclusions have been reached, we will aim to publish this data in a peer-reviewed journal. The journal will be identified at a future date.

**D. Clinical Trials Registration, Results Reporting and Consent Posting**

NA.

**6.5 Secondary Use of the Data**

**7.0 Research Repositories – Specimens and/or Data**

NA

**8.0 Approvals/Authorizations**

- Non- Rutgers Approved study site Approval
- IAA, 1811, 1812a, 830 forms have been uploaded

